### **13.2 Sample size determination**

Sample size has been determined based on preliminary results obtained in our previously published pilot clinical study and statistics obtained in our work.

Sample size has been calculated based on standard deviation values according to methods widely described elsewhere. The major statistical requirements will be pre-specified in our work as follows: significance of probability in one-tailed test will be taken to be 2.5%; the statistical power level will be chosen to be 90%.

With these requirements for sample size determination we decided to enroll a total of 80 volunteers (40 individuals per group).

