**Sample Size**

40 subjects divided into two clinical groups, 20 subjects in each group).

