## **13. STATISTICAL METHODS/DATA ANALYSIS**

### **13.1 Study endpoint**

For assessment of normally distributed parameters the Shapiro-Wilk method will be used. Student's t-test will then be applied for both paired and unpaired samples. Between-group differences at one time point will be evaluated by Wilcoxon-Mann-Whitney test (continuous variables) and Fisher's Exact test (categorical variables). Data analysis will be performed using Stata SE, version 12.1. All statistical tests will be two-sided and statistical significance level alpha will be set at 0.05 for the analysis.

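### The protocol states two unreconciled sample sizes, 40 and 80 subjects; its 90% power is attached only to 80, and neither number can be verified

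*Protocol*

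**What the plan says.** The Sample Size entry of the protocol summary (section 6) reads "40 subjects divided into two clinical groups, 20 subjects in each group". No power or significance level accompanies it.

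Section 13.2 sets two requirements, "significance of probability in one-tailed test will be taken to be 2.5"% and "the statistical power level will be chosen to be 90"%, and then states that on this footing "we decided to enroll a total of 80 volunteers (40 individuals per group". As to where the number comes from, it says only "Sample size has been determined based on preliminary results obtained in our previously published pilot clinical study" and "Sample size has been calculated based on standard deviation values according to methods widely described elsewhere". No difference, SD or endpoint for the calculation is written down.

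For the analysis, section 13.1 says "All statistical tests will be two-sided and statistical significance level alpha will be set at 0.05 for the analysis". Section 17.1 provides for withdrawn volunteers to be replaced. No dropout allowance is stated.

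**The concern.** Both figures are current text, both give a total and a per-group number, and each is consistent within itself (2 × 20 = 40, 2 × 40 = 80). They differ by a factor of two.

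The enrolment target decides when recruitment stops, what the ethics committee has approved and what power the trial can claim. As written, recruitment could end at 40 or at 80 and be called compliant either way. If it ended at 40, the only power statement in the protocol would belong to a trial twice that size. A null result might then be read as firmer evidence against an effect than the design allows.

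**Working it through.** **Inputs.** Group sizes are 20 (summary) and 40 (13.2), allocated 1:1. The level is one-sided 2.5% (13.2) or two-sided 5% (13.1), and power is 90% (13.2). The difference and SD are not stated, so the standardised difference d (difference divided by SD) is an assumption throughout.

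**Can 80 be reproduced?** No. The usual formula is n per group = 2 × (z_α + z_β)² / d², and d is missing. The same holds for 40.

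**Do other statements explain the factor of two?**
- Sidedness: one-sided 2.5% and two-sided 5% share the critical value 1.960, so the difference in wording changes nothing.
- Dropout: none is stated and withdrawals are replaced. To turn 40 into 80 would need a 50% allowance, since 40 / (1 − 0.5) = 80.
- Total versus per group: the summary's 40 is explicitly a total of two groups of 20.

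**The d that each size implies at 90% power.** With z_α + z_β = 1.95996 + 1.28155 = 3.24151 and d = 3.24151 × √(2/n):
- n = 40: 3.24151 × √(2/40) = 0.725 (exact noncentral t: 0.734)
- n = 20: 3.24151 × √(2/20) = 1.025 (exact noncentral t: 1.052)

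**Power if the other size is run.** Power = Φ(d × √(n/2) − 1.960).
- If 40 per group is exactly right for 90%, then at 20 per group: 0.7248 × √10 = 2.292; 2.292 − 1.960 = 0.332; Φ(0.332) = 63% (exact t: 62%).
- If 20 per group is exactly right for 90%, then at 40 per group: 1.0251 × √20 = 4.584; 4.584 − 1.960 = 2.624; Φ(2.624) = 99.6%.

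So the two sizes cannot both be the number needed for 90% power for one effect.

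**Range over assumed d:**

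| d (SD) | 20 per group, normal (exact t) | 40 per group, normal (exact t) |
|---|---|---|
| 0.5 | 35% (34%) | 61% (60%) |
| 0.8 | 72% (69%) | 95% (94%) |
| 1.0 | 89% (87%) | 99% (99%) |

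**Choice of test.** Section 13.1 names the Wilcoxon-Mann-Whitney test for between-group comparison of continuous variables. Under normal data its efficiency relative to the t-test is 0.955. The implied differences then become 0.742 SD (40 per group) and 1.049 SD (20 per group) on the normal approximation. Both sizes are scaled by the same factor, so halving a size that gives 90% still leaves about 63%.

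**The case against.** A reader might infer that 90% power can belong only to 80, or that the summary plans half of what the calculation requires. The document does not support either reading. Section 13.2 shows no calculation, and 20 per group also reaches 90% if the effect is about 1.05 SD or more. The wording reports a decision to enrol 80 and leaves room for that number to exceed the minimum. If it does, the planning effect is larger than 0.73 SD and power at 20 per group is above 62%. The absence of inputs counts equally against both numbers: 80 is no better supported than 40. All of this stands, and it is why the 62% must be conditional.

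It can also be said that the numbers may come from different versions of the design. The summary describes an interventional period ending at the second month, while sections 7.4.2, 7.4.3 and 7.4.6 describe six months, so one planning effect need not apply to both. That is a fair caution about comparing power at the same effect. It does not remove the contradiction, because both sizes stand in one current document as the plan for one trial. The passages on duration must themselves be reconciled; this review takes no view on which is right.

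Finally, the protocol is not silent on a primary endpoint: the summary's Study Design entry names liver size and measures of hepatic lipid accumulation. The gap is narrower: 13.2 does not say which of these the calculation used.

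**Conclusion.** The protocol contradicts itself on its sample size by a factor of two, and this needs no assumption to show. Section 13.2 attaches 90% power to 80 subjects; nothing attaches any power to 40. Neither number can be confirmed or refuted from the document.

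The size of the consequence is conditional. On the assumption that 80 is exactly the number needed for 90% power, with normal data, equal groups and the same effect under either size, a trial of 40 would have about 62% power. Its type II error would be about 38% instead of 10%. Under other assumed effects the loss runs from about 26 percentage points at 0.5 SD (61% to 35%) to about 10 points at 1.0 SD (99% to 89%).

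This is an internal inconsistency that must be corrected. It is not a demonstrated arithmetic error, because no arithmetic is shown that could be wrong.

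**What to change.** State one sample size, total and per group, identically in the summary and in 13.2. In 13.2, name the primary endpoint used for the calculation, give the difference and SD taken from the pilot study and the test assumed, and state the power that the chosen size delivers on those inputs.

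If 80 is the real size, correct the summary. If 40 is the real size, correct 13.2 and keep the 90% figure only if the recomputation supports it.

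The 0.73 SD used above should not be entered as the planning assumption. It is back-solved from 80 and 90%, and writing it in would present a reverse-engineered effect as if the pilot study had supplied it.

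The cost is protocol wording only and, if 40 is the real size, possibly a less favourable stated power.

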### **13.3 Statistical effectiveness analysis**

Statistical analysis of results will be performed by an independent statistician. If the statistical methods and settings listed above are not appropriate for the newly obtained results due to specificity of variant distribution, other methods of statistical analysis will be applied. Any deviations from the statistical plan described above will be explained and justified in a protocol amendment and/or in the final report submitted to the Institutional Ethics Committee.

## **14. QUALITY CONTROL AND QUALITY ASSURANCE**

Independent monitoring of the clinical study for protocol and GCP compliance will be conducted periodically by Institutional Ethics Committee qualified staff from Saratov Institute of Cardiology.

Saratov Institute of Cardiology will permit direct access of study monitors and appropriate regulatory authorities to the study data

and to the corresponding source data and documents to verify the accuracy of the data.

## **15. DATA HANDLING AND RECORD KEEPING**

### **15.1 Data recording/Case Report Forms**

A Case Report Form (CRF) will be completed for each subject enrolled onto the clinical study. The Sponsor-Investigator will review, approve and sign/date each completed CRF; the Sponsor-Investigator's signature serving as attestation of the Sponsor-Investigator's responsibility for ensuring that all clinical and laboratory data entered on the CRF are complete, accurate and authentic.

*Source Data* are the clinical findings and observations, laboratory and test data, and other information contained in *Source Documents*. *Source Documents* are the original records (and certified copies of original records); including, but not limited to, hospital medical records, physician or office charts, physician or nursing notes, subject diaries or evaluation checklists, pharmacy dispensing records, recorded data from automated instruments, x-rays, etc. Where applicable, information recorded on the CRF shall match the *Source Data* recorded on the *Source Documents*.

### **15.2 Record maintenance and retention**

The Sponsor-Investigator will maintain records in accordance with Good Clinical Practice guidelines; to include:

- Financial disclosure information (i.e., for the Sponsor-Investigator and for sub-investigators who will be involved in the administration of the study products and/or the evaluation of research subjects [i.e., who will contribute significantly to the research study data]).
- Curriculum vitae for all participants (i.e., for the Sponsor-Investigator).
- Certificates of required training; e.g., human subject protection, Good Clinical Practice, etc. (i.e., for the Sponsor-Investigator and for all sub-investigators who

will be involved in the administration of the study products and/or the evaluation of research subjects [i.e., who will contribute significantly to the study data]).

- Listing of printed names/signatures. (i.e., for the Sponsor-Investigator and for all sub-investigators who will be involved in the administration of the study products and/or the evaluation of research subjects [i.e., who will contribute significantly to the study data]).
- Normal value(s)/range(s) for medical/laboratory/technical procedures or tests included in the clinical protocol.
- Laboratory certification information.
- Instructions for on-site preparation and handling of the investigational product(s), study treatment(s), and other study-related materials (i.e., if not addressed in the clinical protocol).
- Responsibility delegation log.
- Signed informed consent forms.
- Completed Case Report Forms; signed and dated by Sponsor-Investigator.
- Source Documents or certified copies of Source Documents.
- Monitoring visit reports.
- Copies of Sponsor-Investigator correspondence (including notifications of safety information) to sub-investigators.
- Subject screening and enrollment logs.
- Subject identification code list.
- Investigational product accountability records, including documentation of product disposal.
- Final clinical study report.
- Decoding procedures for blinded studies.
- Master randomization list.

- Retained biological specimen log.
- Interim data analysis report(s).

The Sponsor-Investigator will retain the specified records and reports for up to 5 years.

## **16. ETHICS**

### **16.1 Institutional Review Board (IRB) approval**

The Sponsor-Investigator will obtain from the Institutional Review Board (IRB) of Saratov Institute of Cardiology and Ethics Committee prospective approval of the clinical protocol and corresponding informed consent form(s); modifications to the clinical protocol and corresponding informed consent forms, and advertisements (i.e. directed at potential research subjects) for study recruitment.

### **16.2 Ethical and scientific conduct of the clinical research study**

The clinical research study will be conducted in accordance with the current IRB-approved clinical protocol; ICH GCP guidelines adopted by the FDA; and relevant policies, requirements, and regulations of the Russian Federation and Saratov Institute of Cardiology.

### **16.3 Subject informed consent**

The Sponsor-Investigator will make certain that an appropriate informed consent process is in place to ensure that potential research subjects, or their authorized representatives, are fully informed of the nature and objectives of the clinical study, the potential risks and benefits of study participation, and their rights as research subjects. The Sponsor-Investigator, or sub-investigator(s) designated by the Sponsor-Investigator, will obtain the written, signed informed consent of each subject, or the subject's authorized representative, prior to performing any study-specific procedures on the subject. The date and time that the subject, or the subject's authorized representative, signs the

informed consent form and a narrative of the issues discussed during the informed consent process will be documented in the subject's case history. The Sponsor-Investigator will retain the original copy of the signed informed consent form and a copy will be provided to the subject, or to the subject's authorized representative.

The Sponsor-Investigator will make certain that appropriate processes and procedures are in place to ensure that ongoing questions and concerns of enrolled subjects are adequately addressed and that the subjects are informed of any new information that may affect their decision to continue participation in the clinical study. In the event of substantial changes to the clinical study or the risk-to-benefit ratio of study participation, the Sponsor-Investigator will obtain the informed consent of enrolled subjects for continued participation in the clinical study.

## **17. STUDY DISCONTINUATION CRITERIA**

### **17.1 Discontinuation of individual research subjects**

Individual research subjects can be withdrawn from the study due to occurrence of adverse effects, volunteer's request (regardless of reason) and non-compliance with the protocol. Volunteers withdrawn from the study will be replaced from the pre-screened pool of volunteers.

### **17.2 Sponsor-Investigator discontinuation of the clinical research study**

The clinical study can be terminated by mutual agreement between Sponsor and Investigator for any reason. The Institutional Review Board (IRB) and Ethics Committee of Saratov Institute of Cardiology will be notified promptly of discontinuation of the entire clinical study.

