**Principal Investigator is ultimately responsible for all aspects of the project including:**

A. It is the responsibility of the PI to ensure that each subject is adequately informed and freely consents to participate in the research. The PI will personally ensure that every reasonable

precaution is taken to reduce risks to the study participants, including subjects who are enrolled initially but prove to be screen failures or for whom data is incomplete, unusable, and/or otherwise eliminated during analysis.

B. It is the responsibility of the PI to delegate responsibility to the research staff in a manner that is commensurate with the staff's training and qualifications.

C. It is the responsibility of the PI to ensure that all procedures associated with the research are performed in accordance with the protocol, including the schedule of events as applicable, with the appropriate level of supervision, only by individuals who are licensed or otherwise qualified to perform them under the applicable laws, regulations, and policies.

D. The PI will ensure adherence to the study protocol and monitor the informed consent process.

E. The PI will ensure that there are appropriate facilities and resources to conduct the research.

F. It is the responsibility of the PI to be available to the research staff as needed and to regularly review research processes and address any deficiencies identified through quality improvement processes. The PI may also contact funding partners to schedule an external assessment of his or her research through an on-site visit and a regulatory audit of the protocol file. The PI is responsible for maintaining documentation of any quality improvement process for their specific studies.

G. It is the responsibility of the PI to ensure that adequate staff, resources, and professional practices and standards of care are maintained at external performance sites.

H. It is the responsibility of the PI to evaluate the intermediate and final results of the project and to take a leading role in the preparation of the final report.

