Packages containing the study formulations will be coded and blinded for both the subjects and medical personnel conducting the study. Only the Principal Investigator will be informed of package contents and the subjects belonging to each study group.

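### The protocol contradicts itself on whether the Principal Investigator is blinded, and as written it allows unblinded review of results by group before the study ends

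*Protocol*

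**What the plan says.** **Blinding.** The Study Design text in the Protocol Summary calls the trial double-blinded. It says that neither volunteers nor trial staff will learn the allocation while the study runs, and it leaves unblinding to an independent statistician engaged at the end. Its closing paragraph says the opposite for one person: "Only the Principal Investigator will be informed of package contents and the subjects belonging to each study group".

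**Access and evaluation.** The same text makes each volunteer's results available to the Medical Officer, the Medical Monitor and the PI. Item H of the PI's responsibilities (Key Roles) requires the PI to "evaluate the intermediate and final results of the project".

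**Interim reports.** The list of records to keep in section 15.2 contains the entry "Interim data analysis report(s" (the closing bracket falls outside the quote).

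**Termination.** Section 17.2: "The clinical study can be terminated by mutual agreement between Sponsor and Investigator for any reason".

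**Analysis.** Section 13.1: "All statistical tests will be two-sided and statistical significance level alpha will be set at 0.05 for the analysis". Section 13.3 gives the analysis to an independent statistician. Section 13 mentions no interim comparison.

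**The concern.** Taken together, these rules give one role the allocation, the accumulating results, a duty to evaluate results part-way, and possibly a voice in ending the study. Nothing in the protocol tells that person not to compare the groups early.

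The first thing at stake is the blind. Under section 12 the PI and the Medical Officer determine the cause of adverse events, and under section 8 they share responsibility for dispensing. Someone who knows each subject's group can influence these steps, and others, without intending to. This matters whether or not the trial stops early.

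The second is the type I error. If a favourable look by group ended the trial and the usual 0.05 criterion were then applied, the false-positive rate would exceed 5% and the estimated effect would tend to be exaggerated.

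**Working it through.** **1. The passages side by side**

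| Question | One place | Another place |
|---|---|---|
| Does the PI know the allocation? | No: no trial staff are told (Study Design) | Yes: the PI alone is told (end of Study Design) |
| When is the allocation opened, and by whom? | At the end, by an independent statistician (Study Design) | Already known to the PI during the study (end of Study Design) |
| Are results evaluated before the end? | One analysis, no interim comparison (section 13) | Intermediate results evaluated by the PI (item H); interim reports filed (15.2) |

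The first two rows are direct contradictions. The third is a looseness: item H and section 15.2 anticipate something that section 13 does not describe.

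**2. The stated significance level**

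Section 13.1 uses two-sided 0.05. For the sample size, section 13.2 says "significance of probability in one-tailed test will be taken to be 2.5" per cent. Both give a critical value of 1.960, so they agree. One final test at that cut-off has type I error 0.05, as stated. The figure does not depend on the number of subjects or the length of treatment, so the protocol's inconsistencies on those two matters do not enter.

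**3. What an unadjusted look would do, if one were made**

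The protocol gives no number or timing of looks, so both are assumptions here. With one look at information fraction t, the interim and final statistics are standard normal under the null with correlation √t. If each is tested at 1.960:

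P(false positive) = 0.05 + P(|Z₁| > 1.960 and |Z₂| ≤ 1.960).

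At t = 0.5 the correlation is √0.5 = 0.7071 and the second term is 0.0331, so the total is 0.05 + 0.0331 = 0.0831.

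If the trial stops early only for a result favouring the product, symmetry halves the second term: 0.05 + 0.0331/2 = 0.0666. A simulation with 4 million replicates gave 0.0664.

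| Assumed unadjusted looks before the final test | Stop in either direction | Stop only in favour of the product |
|---|---|---|
| None | 5.0% | 5.0% |
| One, at 25% information | 9.1% | 7.0% |
| One, at 50% | 8.3% | 6.7% |
| One, at 75% | 7.3% | 6.2% |
| Two, equally spaced | 10.7% | 7.9% |

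Stopping for futility, safety or logistics, with no efficacy claim, leaves the rate at or below 5%.

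**The case against.** The strongest reply is that no interim efficacy test exists. Section 13 describes one analysis. The entry in section 15.2 is one line in a generic list of records. Elsewhere the protocol uses *intermediate* for visit time points (Study Design, sections 9 and 11). Section 17.2 is a general termination clause with no link to results, and interim boundaries may be left to a statistical analysis plan that is not at hand. All of this stands. A reader might infer that section 17.2 by itself leaves the 0.05 level unprotected or already inflated, and the documents do not support that.

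Three other tempting inferences also fail:

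- *Each biochemistry visit counts as a look at the primary endpoint.* The Study Design text makes enzymes and lipid parameters the secondary question. Follow-up imaging is scheduled only at the end (Study Design, 7.4.2), although section 11 also mentions liver size at intermediate points. Repeated looks at one biochemical variable say nothing direct about the primary test.
- *Stopping at an unfavourable look adds false positives.* Without an efficacy claim it does not.
- *One party alone decides on termination.* The protocol often uses the combined term Sponsor-Investigator, but 17.2 requires agreement between two parties, and the text at hand does not settle who holds each role.

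The sentence on the PI could also be read as a deliberate exception to the blind. That would remove the contradiction but not the problem, because the excepted person is the one who evaluates results and is responsible for conduct. Nor could an analysis plan repair this, since it does not change who the protocol says holds the allocation.

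**Conclusion.** The point holds as a contradiction about blinding with a conditional consequence for the type I error. The contradiction rests on the text alone. Combined with the PI's access to results and item H, it permits unblinded review by group before the end, and that is enough to put the double-blind claim in doubt.

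The effect on the 5% level depends on an event that the protocol neither plans nor forbids: an unadjusted comparison leading to an early efficacy claim. For one look the rate would be 7.3% to 9.1% if stopping in either direction, and 6.2% to 7.0% if stopping only in favour of the product, depending on the assumed timing. Without such a look it stays at 5%. The protocol should be corrected, mainly to secure the blind.

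**What to change.** 1. **Study Design.** Reconcile the statements on blinding. Have the allocation list held by someone independent of conduct and evaluation, for example the independent statistician, and keep the PI blinded until database lock. The other changes depend on this one, because uncoded review means little to a person who holds the codes.
2. **Key Roles, item H.** State that intermediate results are reviewed only pooled and without group codes until database lock.
3. **Sections 13 and 15.2.** State that no interim comparative efficacy analysis is planned, and remove the interim-report entry. If one is intended, pre-specify its timing, who sees the unblinded results, and a strict boundary. For one look at half the information, O'Brien-Fleming nominal levels of 0.0052 and then 0.0480, or a Pocock level of 0.0294 at both analyses, keep the overall rate at 0.05.
4. **Section 17.2.** The general clause can stay. Add a sentence that unplanned efficacy results by group are not a ground for stopping.

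The cost is a few sentences, with no added patients or procedures. The PI gives up early access to results by group. If a planned look is chosen, the final test runs at a level slightly below 0.05 (O'Brien-Fleming) or clearly below it (Pocock).
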